8.4.1. Descriptive Analysis

Plasma concentrations and PK parameters will be summarized separately by CP and NCI-ODWG hepatic function classification with descriptive statistics (number, arithmetic mean, standard deviation, coefficient of variation [CV%], geometric mean, geometric CV%, median, minimum, and maximum). In addition, summary statistics for protein binding will be tabulated separately by CP and NCI-ODWG hepatic function group.

8.4.2. Statistical Methodology

The primary analysis planned for this study is to evaluate the PK of LOXO-305 after a single dose in subjects with mild, moderate, or severe hepatic impairment, compared to subjects with normal hepatic function. To evaluate the effect of hepatic function group on the PK of a single dose of LOXO-305, paired t-tests will be performed for each hepatic impairment group (by CP classification) versus the normal group with respect to 1-to-1 matching.

In addition, an analysis of covariance (ANCOVA) will be performed on the natural log (In)-transformed AUC_{0-t}, AUC_{0-inf}, and C_{max}. The ANCOVA model will contain a categorical factor of population for subjects with varied-degree hepatic impairment (severe, moderate, and mild by CP classification) and healthy matched-control subjects, a categorical covariate (sex), and continuous covariates (age and BMI). Ratios of least squares means and 90% confidence intervals (CIs) will be calculated using the exponentiation of the difference between hepatic function cohort least squares means from the ANCOVA analyses on the In-transformed AUC_{0-t}, AUC_{0-inf}, and C_{max}. In addition, an ANCOVA will be performed on the natural log (In)-transformed unbound AUC_{0-t}, unbound AUC_{0-inf}, and unbound C_{max}. The specific procedures will be documented in the SAP. Similar ANCOVA analysis will be applied for evaluating the effect of hepatic function group by NCI-ODWG classification.

8.5. Safety Analysis

All safety assessments, including AEs and SAEs, vital sign measurements, clinical laboratory results, physical examination results, concomitant medications, and 12-lead ECGs, will be tabulated and summarized where possible, using descriptive methodology by hepatic function and, as needed, by timepoint. Unless otherwise specified, baseline value is defined as the last non-missing measurement before administration of LOXO-305. No formal statistical analyses are planned for the safety data. All safety data will be listed by subject.

Concomitant medications will be coded using the World Health Organization (WHO) Drug Dictionary (WHO Drug Global B3, September 2019). Adverse events will be coded using Medical Dictionary for Regulatory Activities Version 22.1 (or higher). The incidence of AEs for each hepatic function (matched-control healthy subjects, mild, moderate, and severe) will be presented by severity and by relationship to study drug as determined by the Investigator

or designee (Appendix 1 for AE reporting). All TEAEs will be summarized by system-organ class and preferred term, with a breakdown by hepatic function.

8.6. Data Handling and Record Keeping

Any changes to information in the trial progress notes and other source documents will be initialed and dated on the day the change is made by a CRU staff member authorized to make the change. Changes will be made by striking a single line through erroneous data and clearly entering the correct data (eg, wrong data right data). If the reason for the change is not apparent, a brief explanation for the change will be written adjacent to the change by the CRU staff member.

The Data Management Plan will be approved by the Sponsor.

Data will be validated during data entry by the CRU and verified by the Study Monitor. Data will then be reviewed by the data management group to resolve any outstanding issues. Listings will be generated after the database is cleaned by data management and will be reviewed by the Covance scientific team. The eCRF and ancillary data will be converted into final SAS® datasets following Study Data Tabulation Model or client-provided specifications. The final datasets structure will be verified using Web Submission Data Manager®, while the dataset content will be peer reviewed by an independent programmer.

The tables, figures, and listings (TFLs) will be programmed per the final SAP. All TFLs will be peer reviewed by an independent programmer. In addition, draft TFLs will be reviewed by the Covance scientific team during the dry run and data review meetings.

The peer review will be performed by independent programmers following the quality control process and programming checklists.

8.7. Quality Control and Quality Assurance

Quality control and quality assurance will be performed according to Covance standard operating procedures or per client request, and as applicable, according to the contract between Covance and the Sponsor.

9. ADMINISTRATIVE ASPECTS

9.1. Change in Protocol

There will be no alterations in the protocol without agreement between the Sponsor and the Investigator (or designee).

There will be no alterations in the protocol affecting subject safety without the express written approval of the Sponsor, Investigator (or designee), and the IRB (see Form FDA 1572).

9.2. Site Initiation Visit/Investigator Meeting

Prior to the start of the clinical study, the representative(s) of the Sponsor and/or Covance will meet with the Investigator (or designee) and appropriate CRU staff to familiarize the Investigator (or designee) and CRU staff with the materials necessary for conducting the clinical study.

9.3. Disclosure

All information provided regarding the study, as well as all information collected/documented during the study, will be regarded as confidential. The Investigator (or designee) agrees not to disclose such information in any way without prior written permission from the Sponsor.

Any publication of the results, in part or in total (eg, articles in journals or newspapers, oral presentations, abstracts) by the Investigator (or designee) or their representative(s), shall require prior notification and review, within a reasonable timeframe, by the Sponsor, and cannot be made in violation of the Sponsor's confidentiality restrictions or to the detriment of the Sponsor's intellectual property rights.

9.4. Monitoring

Covance (on behalf of the Sponsor) will designate Study Monitors who will be responsible for monitoring this clinical trial. Covance's Study Monitors will monitor the study conduct, proper eCRF and source documentation completion and retention, and accurate study drug accountability. It is essential that Covance's Study Monitors have access to all documents (related to the study and the individual participants) at any time these are requested. In turn, Covance's Study Monitors will adhere to all requirements for subject confidentiality as outlined in the ICF. The Investigator (or designee) and Investigator's staff will be expected to cooperate with Covance's Study Monitors.

9.5. Institutional Review Board

In accordance with US Title 21 Code of Federal Regulations (CFR) 56, the protocol, advertisement, ICF, and other information provided to subjects will be reviewed and approved by the IRB. The Sponsor will supply relevant material for the Investigator (or designee) to submit to the IRB for the protocol's review and approval. Verification of the IRB unconditional approval of the protocol and the written ICF statement will be transmitted to the Investigator (or designee).

The IRB will be informed by the Investigator (or designee) of subsequent protocol amendments and of serious and unexpected AEs. Approval for protocol amendments will be transmitted in writing to the Investigator (or designee). If requested, the Investigator (or designee) will permit audits by the IRB and regulatory inspections by providing direct access

The Investigator (or designee) will provide the IRB with progress reports at appropriate intervals (not to exceed 1 year) and a Study Progress Report following the completion, termination, or discontinuation of the Investigator's (or designee's) participation in the study.

9.6. Informed Consent

to source data/documents.

Written informed consent for the study will be obtained from all subjects before protocol-specific procedures are carried out. The ICF will be approved (along with the protocol) by the IRB and will be acceptable to the Sponsor.

The Investigator (or designee) will explain the nature of the study and the action of the test product. The subjects will be informed that participation is voluntary and that they can withdraw from the study at any time. In accordance with 21 CFR 50, the informed consent process shall be documented by the use of a written ICF approved by the IRB and signed by the subject prior to protocol-specific procedures being performed.

The subject will sign 2 copies of the ICF. One copy will be given to the subject, and the other will be maintained with the subject's records.

9.7. Records

The results from data collected at Screening and during the study will be recorded in the subject's eCRF. To maintain confidentiality, the subjects will be identified only by numbers.

The completed eCRFs will be transferred to the Sponsor (or designee). Copies of each eCRF will be retained by the Investigator (or designee). All source documents, records, and reports will be retained by the CRU in accordance with 21 CFR 312.62(c).

All primary data, or copies thereof (eg, laboratory records, eCRFs, data sheets, correspondence, photographs, and computer records), which are a result of the original observations and activities of the study and are necessary for the reconstruction and evaluation of any study report, will be retained in the CRU archives.

9.8. Reference to Declaration of Helsinki/Basic Principles

The study procedures outlined in this protocol will be conducted in accordance with the US CFR governing Protection of Human Subjects (21 CFR 50), Financial Disclosure by Clinical Investigators (21 CFR 54), IRBs (21 CFR 56), Investigational New Drug Application (21 CFR 312), Applications for FDA Approval to Market a New Drug (21 CFR 314), and Radioactive Drugs for Certain Research Uses (21 CFR 361.1), as appropriate. As such, these sections of US Title 21 CFR, along with the applicable International Council for Harmonisation (ICH) Guidelines, are commonly known as Good Clinical Practices, which are consistent with the Declaration of Helsinki.

9.9. Financing and Insurance

Financing and insurance will be addressed in a separate agreement.

11. APPENDICES

Appendix 1: Adverse Event Reporting

Adverse Events

Definition of Adverse Events

An adverse event (AE; or adverse experience) is defined as any untoward medical occurrence experienced by a patient or healthy adult subject, whether or not considered drug-related by the Investigator (or designee). A treatment-emergent adverse event (TEAE) is an AE that starts on or after the first administration of study drug.

The following are all AEs:

- unfavorable changes in general condition
- subjective or objective signs/symptoms
- concomitant diseases or accidents
- clinically relevant adverse changes in laboratory parameters observed in a subject during a clinical study.

Adverse events comprise all disturbances of general health status, subjective and objective disease symptoms (including laboratory abnormalities that are deemed clinically significant by the Investigator [or designee]), and accidents observed in the context of a clinical trial, irrespective of a possible causal relationship with the administration of the trial substance.

Categorization of Adverse Events

The severity of AEs will be categorized based on the National Cancer Institute Common Terminology Criteria for Adverse Events (CTCAE) Version 5.0 as follows:

- **Grade 1 Mild:** Asymptomatic or mild symptoms; clinical or diagnostic observations only; intervention not indicated
- **Grade 2 Moderate:** Minimal, local or noninvasive intervention indicated; limiting age-appropriate instrumental Activities of Daily Living (ADL)*
- Grade 3 Severe or medically significant but not immediately life-threatening: Hospitalization or prolongation of hospitalization indicated; disabling; limiting self-care ADL**
- Grade 4 Life-threatening consequences: An event that puts the subject at immediate risk of death
- **Grade 5** Death related to AE.

Note: Not all grades are appropriate for all AEs. Therefore, some AEs are listed within the CTCAE with fewer than 5 options for grade selection. Grade 5 (death) is not appropriate for some AEs and therefore is not an option.

^{*} Instrumental ADL refer to preparing meals, shopping for groceries or clothes, using the telephone, managing money, etc.

^{**}Self-care ADL refer to bathing, dressing and undressing, feeding self, using the toilet, taking medications, and not bedridden.

The Investigator (or designee) will make a determination of the relationship of the AE to the study drug using a 2-category system according to the following guidelines:

- **NOT RELATED** = The time course between the administration of investigational product and the occurrence or worsening of the AE rules out a causal relationship and another cause (eg, concomitant drugs, therapies, complications, comorbidities) is suspected.
- **RELATED** = The time course between administration of investigational product and the occurrence or worsening of the AE is consistent with a causal relationship and no other cause (eg, concomitant drugs, therapies, complications, comorbidities) can be identified.

An AE is associated with the use of the drug if there is a reasonable possibility that the experience may have been caused by the drug.

Pregnancy

As information is available, a pregnancy (including pregnancy in female partners of male subjects) diagnosed through End of Study (EOS) or Early Termination (ET; if the subject discontinues from the study and does not complete a follow-up phone call) and for up to 90 days after Day 1 should be reported by the Investigator (or designee) via email to Covance or the Sponsor's Clinical Safety Representative within 24 hours of being notified. Covance or the Sponsor's Clinical Safety Representative will then forward the Pregnancy Form to the Investigator (or designee) for completion.

email: [contact]

A subject becoming pregnant while on study drug will immediately be withdrawn from the study and ET study procedures will be performed. The subject or partner should be followed by the Investigator (or designee) until completion of the pregnancy. If the pregnancy ends for any reason before the anticipated date, the Investigator (or designee) should notify Covance or the Sponsor's Clinical Safety Representative. At the completion of the pregnancy, the Investigator (or designee) will document the outcome of the pregnancy. If the outcome of the pregnancy meets the criteria for immediate classification as a serious adverse event (SAE; ie, postpartum complication, spontaneous abortion, stillbirth, neonatal death, or congenital anomaly), the Investigator (or designee) should follow the procedures for reporting an SAE.

Male subjects will be instructed to notify the Investigator (or designee) immediately if they discover their sexual partner is pregnant. In this instance, the partner must provide written consent before pregnancy information can be collected. When a Clinical Research Unit (CRU) becomes aware that the female partner of a male subject is pregnant, they are to contact the Investigator (or designee) immediately (within 24 hours of the CRU staff becoming aware of the event) in addition to notifying Covance or the Sponsor's Clinical Safety Representative via email.

All pregnancies should be recorded on the AE electronic Case Report Form (eCRF; as appropriate), in addition to completion of the required pregnancy forms. If the Investigator (or designee) suspects that a pregnancy was the result of an interaction between the study

treatment and the contraceptive method, in addition to the pregnancy the drug interaction should also be captured as a separate AE.

Definition of Serious Adverse Events

An SAE (by Food and Drug Administration [FDA] definition) is any adverse drug experience occurring at any dose that results in any of the following outcomes:

- Death
- A life-threatening adverse drug experience (ie, one that places the subject, in the view of the Investigator [or designee], at immediate risk of death)
- Inpatient hospitalization or prolongation of existing hospitalization
- A persistent or significant disability/incapacity
- A congenital anomaly/birth defect
- An important medical event that may require medical or surgical intervention to prevent one of the above outcomes.

Important medical events that may not result in death, be life-threatening, or require hospitalization may be considered SAEs when, based on appropriate medical judgment, they may jeopardize the patient or subject and may require medical or surgical intervention to prevent one of the outcomes listed in this definition.

Unexpected Adverse Drug Reaction

An AE or suspected adverse drug reaction is considered 'unexpected' if the event is not listed in the Reference Safety Information section of the Investigator's Brochure (IB) or if it is not listed at the specificity or severity that has been observed for an unapproved investigational medicinal product (IMP).

Reporting

Food and Drug Administration-reportable AEs are AEs that are associated with the use of the drug and represent events that are assessed as serious, related, and unexpected. Food and Drug Administration-reportable AEs will be reported by the CRU to the Sponsor and the responsible Institutional Review Board (IRB). Final determination of whether an event represents a suspected unexpected serious adverse reaction (SUSAR) will be the responsibility of the Sponsor.

Within 24 hours of when an AE that is potentially FDA-reportable is first recognized or reported, and within 24 hours of any SAE (regardless of whether the event is assessed as related or unrelated to study drug) being first recognized or reported, Covance or the Sponsor's Clinical Safety Representative will be notified by the Investigator (or designee) in writing using the following email address:

email: [contact]

To report the SAE, the completed report form should be sent by email to Covance or the Sponsor's Clinical Safety Representative within 24 hours of awareness. Incoming reports are

reviewed during normal business hours. Additional reporting instructions and the SAE Report Form are provided in the Study Manual.

The IRB will be notified of any FDA-reportable AE within the timeframe required by the IRB. The IRB Serious and Unexpected Adverse Experience Submission Form will be completed and submitted with the copy of the written confirmation or summary of the AE.

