7.2.1. Adverse Events

Adverse event definitions; assignment of severity, causality, action taken, and outcome; and procedures for reporting SAEs are detailed in Appendix 1.

Subjects will be asked a non-leading HDYF? Question such as "Have there been any changes in your health status since Screening/since you were last asked?" at the timepoints specified in Appendix 4 (ie, at Screening [after the ICF is signed], at Check-in [Day -1], at each postdose vital sign measurements, and at an appropriate time for all other days). Subjects will also be encouraged to voluntarily report AEs occurring at any other time through the EOS.

Adverse events, whether volunteered, identified by the subject's responses to HDYF? Inquiries, or noted on physical examination, ECG, vital sign measurements, or clinical laboratory evaluations, will be recorded throughout the study (ie, from signing of the ICF until EOS [or ET if the subject discontinues from the study and does not complete a follow-up phone call]), either as subject medical history (if the event is reported as beginning prior to signing of the ICF or if the event occurs prior to study drug administration on Day 1 and is assessed as not related to study procedures by the Investigator [or designee]) or as AEs (if the event occurs after signing of the ICF but prior to study drug administration on Day 1 and is assessed as related to study procedures by the Investigator [or designee], or if the event occurs after study drug administration on Day 1 through EOT or ET regardless of relationship to study drug). From EOT or ET through EOS, only AEs assessed as related to study drug by the Investigator (or designee) are to be reported. All SAEs that develop from the time of ICF signing until EOS (or ET, if the subject discontinues from the study and does not complete a follow-up phone call) are to be reported.

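### Appendix 1's RELATED and NOT RELATED definitions do not cover an AE with compatible timing and an identified other cause, so related-AE tables by hepatic group may not be comparable

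*Protocol*

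**What the plan says.** Protocol Appendix 1 has the investigator decide relationship to study drug "using a 2-category system according to the following guidelines". Each of the two categories joins two conditions:

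- RELATED: the time course "is consistent with a causal relationship and no other cause (eg, concomitant drugs, therapies, complications, comorbidities) can be identified".
- NOT RELATED: the time course "rules out a causal relationship and another cause (eg, concomitant drugs, therapies, complications, comorbidities) is suspected".

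The appendix then sets a separate standard. An AE is associated with the drug "if there is a reasonable possibility that the experience may have been caused by the drug". That sentence is not tied to either category. The Reporting paragraph uses both ideas together, defining FDA-reportable AEs as "AEs that are associated with the use of the drug and represent events that are assessed as serious, related, and unexpected".

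The label is used downstream in two ways. Under Protocol 8.5, AE incidence for each hepatic function group "will be presented by severity and by relationship to study drug as determined by the Investigator" or designee, with a pointer to Appendix 1. SAP 8.6.1 takes the investigator's label as recorded, tabulates treatment-related TEAEs by hepatic function group, and counts a TEAE with a missing relationship as related. Protocol 7.2.1 also makes late reporting depend on the label: "From EOT or ET through EOS, only AEs assessed as related to study drug by the Investigator (or designee) are to be reported". SAEs are exempt from that restriction.

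**The concern.** A two-category scale needs each category to be the negation of the other. Here each is a conjunction, and the two do not even use the same test for another cause: one asks whether it can be identified, the other whether it is suspected. An event that satisfies one half of each definition has no stated home.

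The trial compares groups that differ in exactly the other causes the definitions name. Impaired subjects must have a known history of liver disease (Protocol 4.3, criterion 9) and may take medication to stabilise their condition (6.1). Matched controls are excluded for significant disorders across most organ systems (4.4, criterion 29). If the undefined events arise more often in the impaired groups, or are labelled differently by different investigators in this multi-center study, a difference between groups in related AEs could reflect labelling and not the drug.

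**Working it through.** **Step 1: list the combinations.** Take timing as compatible or ruled out, and other cause as none, suspected only, or identified. Apply the two definitions literally.

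| Timing | Other cause | Category |
|---|---|---|
| Compatible | None | RELATED |
| Compatible | Suspected only | RELATED (none is identified) |
| Compatible | Identified | Neither |
| Ruled out | None | Neither |
| Ruled out | Suspected only | NOT RELATED |
| Ruled out | Identified | NOT RELATED |

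Two of 6 cells have no category. If suspected and identified are treated as the same, the count is 2 of 4. The cell with ruled-out timing and no other cause is a formal gap only, since nobody would call such an event related. The material gap is compatible timing with an identified other cause. These are counts of cells, not of events.

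**Step 2: see whether another sentence closes the material gap.**

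- The reasonable-possibility sentence defines association, not RELATED. A gap event can meet it and still fail RELATED, while the FDA-reportable definition asks for both.
- The SAP rule for a missing relationship acts only on a blank field. An investigator who must choose a category leaves no blank.
- The Study Manual, which Appendix 1 cites for additional reporting instructions, is not among the documents reviewed.

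**Step 3: show how labelling alone could move a table.** All inputs here are assumptions, not figures for this drug: 8 subjects per group, the same 25% risk of a timing-compatible AE in each, and another cause identified for 0 to 10% of such events in controls and 30 to 80% in impaired subjects.

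- Expected subjects with such an AE: 8 × 0.25 = 2.0 per group.
- Gap events labelled NOT RELATED: controls 2.0 × (1 − 0.10) = 1.8 to 2.0 × (1 − 0) = 2.0; impaired 2.0 × (1 − 0.80) = 0.4 to 2.0 × (1 − 0.30) = 1.4.
- Gap events labelled RELATED: 2.0 in both groups.

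The same events give equal groups or unequal groups depending on a choice that the protocol does not define. This shows the mechanism and is not an estimate.

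**Step 4: trace the late-reporting effect.** After EOT or ET, a non-serious gap event labelled NOT RELATED is not reported. The follow-up call itself is open: Appendix 4 schedules the general health inquiry (HDYF?) and AE/SAE collection at that contact. Only reporting is filtered. That filter is a separate rule that would operate under any two-category definition, and the gap adds few events to it.

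**The case against.** The strongest reply is that the definitions are only guidelines. The investigator makes the determination, and the reasonable-possibility sentence follows directly and could settle a mixed case. It stands that every event will receive a label. It does not make the label consistent: these are the only causality criteria in the protocol, and that sentence is not linked to the two categories.

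Second, the group imbalance is unquantified. Impaired subjects must be clinically stable for at least 1 month before Screening and on a stable regimen for 14 days before Day 1 (Protocol 4.3), which limits new events from background disease or medication. This stands as a limit on size. It does not remove the contrast with controls screened for significant disorders.

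Third, safety is a secondary objective, no inferential safety analysis is planned (SAP 8.6.6), and no decision rule in the documents uses the related-TEAE tables. This stands and keeps the point at moderate weight.

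A reader might infer three stronger things that the documents do not support:

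- That the follow-up call seeks only SAEs and drug-related AEs. Section 7.2.1 states the purpose of the call in those terms, but Appendix 4 schedules an open inquiry.
- That serious events would escape notification. All SAEs are notified within 24 hours whatever the assessed relationship, as are potentially FDA-reportable AEs. In addition, "Final determination of whether an event represents a suspected unexpected serious adverse reaction (SUSAR) will be the responsibility of the Sponsor".
- That related AEs will be understated in impaired subjects. That needs gap events to be more frequent there and to be labelled NOT RELATED, and the documents establish neither.

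**Conclusion.** The wording defect is real, and confidence in it is high: on the literal text, an AE with compatible timing and an identified other cause is neither RELATED nor NOT RELATED, and nothing in the protocol or SAP assigns it. The consequence is that AE incidence by relationship and treatment-related TEAE tables may not be comparable across hepatic groups. Confidence in the size of that effect is low. It rests on the plausible but unmeasured assumption that other causes are identified more often in impaired subjects, or that investigators resolve the gap differently. Neither frequency nor direction can be computed from the documents. The effect on reporting after EOT or ET is secondary and narrow.

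The following do not depend on the gap: all-causality TEAE tables up to EOT or ET, listings of recorded AEs, SAE reporting and notification, the Sponsor's SUSAR determination, and the PK analysis. The point should be corrected because the repair is small, not because it threatens the primary objective.

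**What to change.** Redefine the two categories in Appendix 1 as complements of the standard it already contains:

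- RELATED: there is a reasonable possibility that the drug caused the event. Another identified cause does not by itself exclude this.
- NOT RELATED: there is no reasonable possibility that the drug caused the event.

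Use that single term in the FDA-reportable sentence in place of the present pairing of associated and related. The SAP tables need no change, since they take the investigator's label as given.

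The cost is a short protocol amendment, with Sponsor and investigator agreement (Protocol 9.1) and IRB handling (9.5). The Study Manual needs a matching edit if it repeats the definitions. AEs already assessed may need re-review so that one rule applies to all subjects. The count of related events may rise, by an amount that the documents do not allow anyone to predict.
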